6.2.2.1.3 Rules for Dose Withholding

AMG 176 should be withheld for any of the following:

- Suspected DLT (including adverse events that meet DLT definition outside DLT observation period).
- Aspartate aminotransferase or ALT greater than 3 x ULN or total bilirubin greater than 1.5 x ULN.
- Any grade 3 arrhythmia deemed possibly related to AMG 176. Should dosing be resumed, AMG 176 should be given at the next lower dose level.
- Any central lab elevation of cardiac troponin > 0.1 ng/mL (ADVIA Centaur XP Tnl manufacturer's prognostic cut-off) and < 0.78 ng/mL, OR any change in the clinical status, above lab analytes (central or locally obtained), ECHO, or ECG deemed significant by the investigator or study subjects' care team.
 - Upon meeting withholding criteria for AMG 176, investigator/site physician should evaluate appropriateness of apparent benefit vs risk of re-initiating AMG 176.
 Based on the assessment, a subject may be continued drug at a reduced dose or permanently discontinue therapy.
- Low elevations from 0.04 to ≤ 0.1 ng/mL do not require withholding or dose reductions, though troponins should be monitored with subsequent doses.
- Elevations from > 0.1 to < 0.78 ng/mL should result in a dose withholding, and if further treatment is considered, should be restarted at one dose level below the dose where elevated troponins were observed.
- Permanently discontinue AMG 176 for elevations ≥ 0.78 ng/mL.
 - Any consideration for continued treatment of AMG 176 after troponin elevations will require discussion between the investigator, subject, and Amgen medical monitor, and following normalization of all abnormalities.
 - Study subjects that meet withholding criteria require continuous cardiac monitoring (telemetry) for at least 24 hours, and a cardiologist's evaluation that includes transthoracic echocardiography to assess the study subject and provide recommendations for further cardiac care. Monitoring should continue according to local SOC.

6.2.2.1.4 Rules for Restarting

AMG 176 dosing can be resumed:

- If the adverse event resolves to grade ≤ 1 or return to subjects' baseline values.
 - For subjects meeting the withholding criteria for elevation of cardiac troponin (> 0.1 to < 0.78 ng/mL), AMG 176 dosing can be resumed at the immediate next lower dose level if the requirements mentioned above in Rules for Dose Withholding are met.
- If the restarting of therapy should be deemed safe by the investigators and Amgen's Medical Monitor.

Protocol Number: 20200392

Date: 28 April 2022 Page 67 of 149

6.2.2.1.5 Rules for Permanent Discontinuation

Subjects will permanently discontinue from the investigational product if the following are observed:

- Subjects experience adverse events meeting the DLT criteria at any time. Subjects
 will be followed until the DLT is resolved, returns to baseline value or is considered
 stable. Subjects will be withdrawn from AMG 176 treatment and will be treated as
 deemed appropriate by the investigator or treating physician. Except for:
 - Subjects showing evidence of response or subjects who in the opinion of the investigator may be responding to AMG 176, may have the option to continue therapy once the adverse events recover to baseline or grade 1 and the re-introduction of AMG 176 is deemed safe by the investigator, and Amgen's Medical Monitor. The subject should restart at a reduced dose.
- Intolerability of AMG 176.
- Grade 3 central laboratory elevations of troponin.
- Any Grade 4 arrhythmia possibly associated with AMG 176.
- Symptoms of clinically significant cardiac dysfunction (defined in Table 6-2), ECG changes, or diagnostic evidence of decreased cardiac function or cardiac injury irrespective of any cardiac troponin level (centrally or locally obtained). Study subjects that meet permanent discontinuation criteria require continuous cardiac monitoring (telemetry) for at least 24 hours, and a cardiologist evaluation that includes transthoracic echocardiography to assess the study subject and provide recommendations for further cardiac care. Monitoring should continue according to local SOC.
- Hepatotoxicity (as defined in Section 11.7).

The dosing is delayed > 4 weeks due to AMG 176-related adverse events.

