Investigators should, whenever possible, determine which medication is causing the toxicity and interrupt or dose reduce azacitidine and/or AMG 176, as applicable. Dose reductions will be as per Table 6-3 recommendations. Dose reductions different than Table 6-3 are allowed if determined to be in the patient's best interest and rationale documented in patient record. The investigators will use their clinical judgment to determine whether toxicity is caused by azacitidine, AMG 176, or both. Dose reductions of one of the agents, or both, are allowed after discussion with the PI or co-PI and documentation in the medical record.

Protocol Number: 20200392

Date: 28 April 2022 Page 64 of 149

Table 6-3. Dose Adjustments for Non-hematologic AEs That Are at Least Possibly Related

| Grade | Occurrence | Dose Modification | | |
|--|-----------------------|---|--|--|
| 1 or 2 | Anytime | No dose reduction | | |
| 3 or 4 Persistent grade 2: consider similar dose adjustments if persistent and not responding to optimal management in the opinion of PI and treating physician | First and second time | Hold AMG 176 ± azacitidine. Resume AMG 176 ± azacitidine a prior dose if recovery to ≤ grade 1 occurs within 14 days. If toxicity persists for 15 to 28 days, hold therapy and resume azacitidine and AMG 176 at prior dose if recovery to ≤ grade 1 or resume AMG 176 ± azacitidine at ONE dose level below current dose if recovery to ≤ grade 2. | | |
| | Third and fourth time | Hold AMG 176 ± azacitidine. Follow until toxicity ≤ grade 2. Resume AMG 176 ± azacitidine at ONE dose level below current dose. | | |
| | Fifth time | Hold AMG 176 ± azacitidine. Follow until toxicity ≤ grade 2. Resume AMG 176 ± azacitidine at TWO dose levels below current dose. | | |

PI = Principal Investigator.

Other Modifications of Dose Schedules

- Further dose reductions can be made to prevent adverse events and keep clinically significant toxicities grade ≤ 2.
- Dose adjustments by more than one dose level at a time can be considered when judged in the best interest of the patient (eg, severe myelosuppression) when toxicity has resolved. The reason for this reduction will be discussed with the PI or co-PI and documented in the medical record.
- Treatment interruptions and dose modifications other than the ones mentioned above
 can be considered after discussion with the PI and proper documentation of the
 rationale. Dose adjustment/delay of only one of the agents is permissible if the toxicity

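### Table 6-3 conflicts with the AMG 176-specific dosing rules for three groups of related events, and no visible text says which governs

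*Protocol*

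**What the plan says.** Protocol Section 6.2.2 says of non-hematologic toxicity: "Dose reductions will be as per Table 6-3 recommendations". Table 6-3 applies to every non-hematologic event that is at least possibly related. It has no exclusion for DLTs, life-threatening events, arrhythmia or troponin. For a first or second grade 3 or 4 event, AMG 176 is held and then: "Resume AMG 176 ± azacitidine a prior dose if recovery to ≤ grade 1 occurs within 14 days" (meaning at the prior dose). If the toxicity lasts 15 to 28 days, recovery to grade 1 or less again leads to the prior dose; otherwise the instruction is "resume AMG 176 ± azacitidine at ONE dose level below current dose if recovery to ≤ grade 2". The lowest row reads "1 or 2 | Anytime | No dose reduction".

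The AMG 176 sections set their own rules:

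- Section 6.2.2.1.5 lists the triggers for permanent discontinuation. They include "Subjects experience adverse events meeting the DLT criteria at any time", "Grade 3 central laboratory elevations of troponin" and "Any Grade 4 arrhythmia possibly associated with AMG 176". Subjects who are or may be responding can continue after recovery to baseline or grade 1, but "The subject should restart at a reduced dose".
- Section 6.2.2.1.1 bars rechallenge after a related life-threatening event and sends a grade 3 arrhythmia to the next lower level. Sections 6.2.2.1.3 and 6.2.2.2.2 repeat the arrhythmia reduction.
- Section 6.2.2.1.3 stops AMG 176 at troponin of 0.78 ng/mL or more. Above 0.1 and below 0.78 ng/mL it withholds AMG 176 and restarts one level lower.
- Section 6.2.2.1.4 allows restart only at grade 1 or baseline, and only if the investigators and the Medical Monitor judge it safe.

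**The concern.** The same event can fall under both sets of rules. A site that follows Table 6-3 as written could restart AMG 176 at full dose in a subject whom another section says must stop or be reduced. Increased troponin is an identified risk of AMG 176 and cardiovascular toxicity a potential one (Section 2.3.2), so the overlap includes events that the cardiac monitoring plan was written to catch. Two sites could also handle the same event differently and each claim to have followed the protocol.

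**Working it through.** No arithmetic applies. The check sets the rules side by side.

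**Step 1: do the scopes overlap?** Yes. Under Sections 6.2.1.2 and 6.2.1.2.1 and Table 6-2, a DLT is largely an AMG 176-related non-hematologic event of grade 3 or more, outside listed exceptions. Section 6.2.2.1.5 applies the DLT criteria at any time, not only in cycle 1. For troponin, Section 6.2.1.2.2 defines only two grades: grade 1 above 0.04 ng/mL (females) or 0.059 ng/mL (males), and grade 3 at 0.78 ng/mL or more. Values above 0.1 and below 0.78 ng/mL exceed both upper reference limits without reaching grade 3, so they are grade 1. Section 8.4.3 counts a laboratory change that requires therapy adjustment as an adverse event, so Table 6-3 can apply to that band.

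**Step 2: do the actions differ?** Rows (a) and (b) assume a first or second occurrence that has recovered to grade 1 or less within 28 days.

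| AMG 176-related event | Table 6-3 | AMG 176 rules |
|---|---|---|
| (a) Meets DLT criteria | Prior dose | Stop; reduced dose if possibly responding (6.2.2.1.5) |
| (a) of which grade 3 arrhythmia | Prior dose | Next lower level (6.2.2.1.1, 6.2.2.1.3, 6.2.2.2.2) |
| (a) of which grade 4 arrhythmia | Prior dose | Stop (6.2.2.1.5, 6.2.2.2.2) |
| (a) of which troponin ≥ 0.78 ng/mL | Prior dose | Stop (6.2.2.1.3, 6.2.2.1.5) |
| (b) Life-threatening | Prior dose | No rechallenge (6.2.2.1.1) |
| (c) Troponin > 0.1 and < 0.78 ng/mL | No dose reduction | Withhold; restart one level lower (6.2.2.1.3, 6.2.2.1.4) |

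The arrhythmia and high-troponin rows are parts of group (a). Grade 3 troponin is itself listed in Table 6-2, and a related grade 3 or 4 arrhythmia generally meets its grade 3 criterion. That leaves three independent conflicts. For grade 3 arrhythmia the AMG 176 sections give two answers (stop as a DLT, or next lower level), but neither is the prior dose.

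**Step 3: does the restart grade differ?** In part. At 15 to 28 days Table 6-3 accepts grade 2 with a one-level reduction, while Sections 6.2.2.1.4 and 6.2.2.1.5 require grade 1 or baseline. But Section 6.2.2.2.3 lets AMG 176 restart after grade 3 or 4 gastrointestinal toxicity once it has improved to grade 2, with no reduction stated. The restart threshold is therefore not uniform within the AMG 176 rules. The separate bar on rechallenge for persistent grade 3 events takes effect only after 4 weeks, so it does not add a conflict inside the 28-day window.

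**Step 4: does any text rank the two?** None that is visible. Section 6.2.2 permits documented departures from Table 6-3 by judgment, which is discretion and not precedence. Duration of Therapy in Section 4.1.2 conditions continued treatment on there being no event that requires permanent discontinuation, but does not mention the table. Section 6.6 routes troponin management to Sections 6.2.2.1 and 6.2.2.2.5, but only in the context of overdose.

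**The case against.** The strongest reply is that the specific rule governs the general one. The discontinuation and arrhythmia rules are written for AMG 176 in mandatory terms, while Table 6-3 is a set of recommendations from which departures are allowed. Most experienced investigators would apply the stricter text.

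There are also safeguards. Section 6.2.2.1.4 makes Medical Monitor agreement a condition of restart. Footnote a of Table 6-2 asks for a cardiology evaluation and Medical Monitor discussion before further treatment after grade 1 troponin. Section 6.2.2.1.3 requires discussion between investigator, subject and Medical Monitor before continuing after a troponin elevation.

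Much of this stands, and it limits the practical risk. It does not remove the conflict. That the specific rule governs is an inference the protocol does not state, and permission to be stricter is not a requirement to stop. Section 6.2.2.1.4 names a restart dose only for troponin, so for the other events the Medical Monitor faces the same two texts.

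It is also fair to say that early termination (SAP Section 7.1), with Part 2 never enrolled (SAP Section 3.1), leaves little to act on beyond reporting.

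**Conclusion.** The inconsistency is real and limited to the three groups (a) to (c). It is a minor to should-fix safety point. No sample size, estimate or error rate depends on it.

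Four stronger readings are tempting, and the documents do not support them:

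- A reader might infer that Table 6-3 is always the laxer rule. Section 6.2.2.2.3 is more permissive than the table for gastrointestinal events.
- A reader might count each arrhythmia and troponin rule as a separate contradiction. Most of them fall inside the DLT group.
- A reader might conclude that resuming at the prior dose after any grade 3 or 4 event breaches the protocol. Events within the Table 6-2 exceptions do not trigger the DLT stopping rule. Events attributed to azacitidine alone are not DLTs under Section 6.2.1.2.
- A reader might infer that subjects were dosed unsafely. Neither document says so.

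The conclusion rests on two assumptions: that a troponin value in band (c) is recorded as an adverse event at least possibly related to treatment, and that nothing in Section 6.1.1 (Table 6-1), whose content is absent from the supplied text, settles precedence.

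**What to change.** Add one statement to Section 6.2.2 and repeat it under Table 6-3:

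> For events attributed at least possibly to AMG 176, Sections 6.2.2.1.1 to 6.2.2.1.5 and 6.2.2.2.2 take precedence over Table 6-3 for AMG 176 dosing. Table 6-3 applies to AMG 176 only where those sections do not require withholding, a lower dose or discontinuation.

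Also state whether the grade 2 restart threshold in Section 6.2.2.2.3 is an exception to Section 6.2.2.1.4 for gastrointestinal events. Prior-dose resumption should not be confined to events within the DLT exceptions, because that would also catch azacitidine-attributed events.

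Since the trial has closed, the clinical study report should state which rule was applied to any affected subject. The listings planned in SAP Sections 9.6.2 (adverse events, DLTs, troponin events) and 9.6.8 (planned and actual dose, reason for change) will identify those subjects. They will not show which rule was followed, and SAP Section 9.3 provides no deviation listing, so dosing records need a short check. The cost is two sentences of protocol text, or one statement in the report plus that check.

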6.2.2.2 AMG 176 Management of Toxicities

6.2.2.2.1 Management of Infections

Subjects with evidence of existing infection should be closely monitored while being treated with AMG 176. Subjects with active systemic infections requiring IV antibiotics, antivirals, or antifungals should not be dosed with AMG 176 until infection has resolved and if being treated with an anti-infectious therapy, the course of such therapy should have been completed. Management should be tailored to the appropriate prophylaxis and/or treatment for the underlying infection according to the local SOC and institutional guidelines with the exception of excluded medications detailed in Section 6.1.7.

Infection Prophylaxis

Subjects who may experience neutropenia are at a high risk for infectious complications. As appropriate, these subjects should be administered prophylactic antibacterial (eg, treatment with ciprofloxacin) and antifungal (treatment with amphotericin B or echinocandins).

Protocol Number: 20200392

Date: 28 April 2022 Page 68 of 149

These subjects should be monitored for early signs of breakthrough infections after the initiation of antibacterial therapy to prompt additional evaluation and possible therapy modification. Subjects experiencing diarrhea should be closely monitored for their electrolyte levels.

6.2.2.2.2 Management of Cardiac Arrhythmia

Subjects with risk factors for, or evidence of, existing heart disease should be closely monitored throughout their treatment with AMG 176. Subjects should be clinically monitored on ongoing basis for cardiac function (blood pressure, heart rate, ECHO, and ECG) according to the Schedule of Activities (see Section 1.3). The administration of AMG 176 should be withheld if grade 3 or 4 arrhythmias (including tachycardia) develop or appear to be exacerbated by AMG 176 treatment. For any grade 3 arrhythmia related to AMG 176 administration, the AMG 176 dose should be reduced. Treatment may be resumed once the signs and symptoms resolve to baseline value or grade 1.

Management should be tailored to the appropriate treatment for the underlying cardiac disorder according to the local SOC and institutional guidelines. For any grade 4 arrhythmia related to AMG 176 administration, AMG 176 should be permanently discontinued.

6.2.2.2.3 Management of Gastrointestinal Toxicities

Nausea, vomiting, and diarrhea have been observed in a phase 1 FIH dose finding study (Study 20150161). AMG 176 must be withheld from subjects with grade 3 or 4 gastrointestinal toxicity at any time during study treatment participation. Management should be tailored to the appropriate treatment according to the local SOC and institutional guidelines. AMG 176 can be restarted when the toxicity has improved to at least a grade 2.

6.2.2.2.4 Prophylaxis and Management of Tumor Lysis Syndrome Refer to Section 11.9 for guidance.

6.2.2.2.5 Management of Troponin and Other Cardiac Enzymes Elevation Subjects with risk factors for, or evidence of, existing heart disease should be closely monitored throughout their treatment with AMG 176. Subjects should be clinically monitored with local and central cardiac monitoring tests for elevated troponin and cardiac enzymes diagnostic of cardiac injury. Local troponin testing will be performed to guide immediate clinical care. Central testing of troponin-I with ADVIA Centaur XP TnI assay will be performed for all screening, grading, and withholding decisions.

Protocol Number: 20200392

Date: 28 April 2022 Page 69 of 149

6.2.2.3 Amgen/Non-Amgen Non-Investigational Product: Azacitidine

The reason for dose change of azacitidine is to be recorded on each subject's CRF(s). For contraindications, warnings, precautions, and potential drug interactions please refer to the current prescribing information for azacitidine.

Azacitidine dose adjustments based on hematology laboratory values:

Hematological toxicity is defined as the lowest count reached in a given cycle (nadir) if platelets ≤ 50.0 x 10⁹/L and/or ANC ≤ 1 x 10⁹/L.

Recovery is defined as an increase of cell line(s) where hematological toxicity was observed of at least half of the difference of nadir and the baseline count plus the nadir count (ie, blood count at recovery \geq to nadir count + (0.5 x [baseline count - nadir count]).

• Subjects without reduced baseline blood counts (ie, White Blood Cells [WBC] $\geq 3.0 \times 10^9$ /L and ANC $\geq 1.5 \times 10^9$ /L, and platelets $\geq 75.0 \times 10^9$ /L) prior to the first treatment.

For subjects with baseline (start of treatment) WBC \geq 3.0 x 10⁹/L, ANC \geq 1.5 x 10⁹/L, and PLT \geq 75.0 x 10⁹/L, adjust the dose as follows, based on nadir counts for any given cycle (see Table 6-4):

Table 6-4. Azacitidine Hematology Dose Reduction Guidance

| Nadir counts | | |
|----------------------------|----------------------------------|--------------------------|
| ANC (x 10 ⁹ /L) | Platelets (x 10 ⁹ /L) | % Dose in the Next Cycle |
| < 0.5 | < 25.0 | 50% |
| 0.5 to 1.5 | 25.0 to 50.0 | 67% |
| > 1.5 | > 50.0 | 100% |

ANC = absolute neutrophil count.

For patients whose baseline counts are WBC $< 3.0 \times 10^9$ /L, ANC $< 1.5 \times 10^9$ /L, or platelets $< 75.0 \times 10^9$ /L, dose adjustments should be based on nadir counts and bone marrow biopsy cellularity at the time of the nadir as noted below (see Table 6-5), unless there is clear improvement in differentiation (percentage of mature granulocytes is higher and ANC is higher than at onset of that course) at the time of the next cycle, in which case the dose of the current treatment should be continued.

Protocol Number: 20200392

Date: 28 April 2022 Page 70 of 149

Table 6-5. Azacitidine Dose Reduction Based on Bone Marrow Cellularity

| WBC or Platelet Nadir % — | Bone Marrow Biopsy Cellularity at Time of Nadir (%) | | | |
|----------------------------------|---|----------|------|--|
| decrease in counts from baseline | 30 to 60 | 15 to 30 | < 15 | |
| | % Dose in the Next Cycle | | | |
| 50 to 75 | 100 | 50 | 33 | |
| > 75 | 75 | 50 | 33 | |

WBC = white blood cell

If a nadir as defined in the table above has occurred, the next course of treatment should be given 28 days after the start of the preceding course, provided that both the WBC and the platelet counts are > 25% above the nadir and rising. If a > 25% increase above the nadir is not seen by day 28, counts should be reassessed every 7 days. If a 25% increase is not seen by day 42, then the subject should be treated with 50% of the scheduled dose.

Following dose modifications, a new cycle will be started and duration should return to 28 days.

Dose adjustment based on renal function and serum electrolytes:

- Unexplained reduction of sodium bicarbonate to < 20 mEq/L reduce dose by 50% on the next cycle
- Unexplained elevation of Blood Urea Nitrogen (BUN) or serum creatinine ≥ 2-fold above baseline - delay next cycle until values return to normal or baseline and dose reduce by 50% in the next treatment cycle.

